The E-RS is a PRO instrument derived from the EXACT-PRO designed to collect data to quantify the severity of respiratory symptoms across domains of breathlessness, chest symptoms and cough/sputum in patients with COPD and evaluate treatment benefit (EXACT 2013). The E-RS is an electronic instrument to be completed by the patient in the form of the EXACT-PRO in the eDiary each evening before bedtime.

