6.4. WINDOWING CONVENTIONS

Each visit (except for Day 1 visit) will have a ± 10 days window. No visit windowing will be applied during the analysis to the data that is only collected at scheduled site visits for patients that have completed the study, and therefore the data will be presented as per the visit reported in the database.

For the patients that discontinued from the study, the End of Study (EOS) visit will be windowed to the corresponding visit, based on the study day, for questionnaire, spirometry and rescue medication data. The EOS visit can only be windowed to a visit that is missing or has a missing result. The rules for the windowing are described below.

- For spirometry raw data and derived data that happens at every visit, windowing will be done as per the corresponding visits.

- Day 1 = Day 1
 - Week 6 = after Day 1 and up to and including Day 53
 - Week 12 = after Day 53 and up to and including Day 95
 - Week 24 = after Day 95 and up to and including Day 179
- For spirometry derived data that only happen at certain visits, windowing will be done for the corresponding visits.
 - For morning trough:
 - Week 6 = after Day 1 and up to and including Day 53
 - Week 12 = after Day 53 and up to and including Day 95
 - Week 24 = after Day 95 and up to and including Day 179
 - For evening trough and AUC_{0-12h}:
 - Week 12 = after Day 1 and up to and including Day 95
- For rescue medication data, E-RS/EXACT-PRO, e-diary data and COPD exacerbation, windowing will be done as per the corresponding visits.
 - For patients who completed the study or who discontinued study medication but continue in the study:
 - Week 1 = Actual study Day of Week 24 visit minus 168 days (inclusive) up to and including actual study day of week 24 visit minus 161 days
 - Week 2 = Actual study Day of Week 24 visit minus 161 days up to and including actual study day of week 24 visit minus 154 days
 - Week 3 = Actual study Day of Week 24 visit minus 154 days up to and including actual study day of week 24 visit minus 147 days
 - Week 4 = Actual study Day of Week 24 visit minus 147 days up to and including actual study day of week 24 visit minus 140 days
 - Week 5 = Actual study Day of Week 24 visit minus 140 days up to and including actual study day of week 24 visit minus 133 days
 - Week 6 = Actual study Day of Week 24 visit minus 133 days up to and including actual study day of week 24 visit minus 126 days

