 - Week 7 = Actual study Day of Week 24 visit minus 126 days up to and including actual study day of week 24 visit minus 119 days
 - Week 8 = Actual study Day of Week 24 visit minus 119 days up to and including actual study day of week 24 visit minus 112 days
 - Week 9 = Actual study Day of Week 24 visit minus 112 days up to and including actual study day of week 24 visit minus 105 days
 - Week 10 = Actual study Day of Week 24 visit minus 105 days up to and including actual study day of week 24 visit minus 98 days
 - Week 11 = Actual study Day of Week 24 visit minus 98 days up to and

- including actual study day of week 24 visit minus 91 days
- Week 12 = Actual study Day of Week 24 visit minus 91 days up to and including actual study day of week 24 visit minus 84 days
- Week 13 = Actual study Day of Week 24 visit minus 84 days up to and including actual study day of week 24 visit minus 77 days
- Week 14 = Actual study Day of Week 24 visit minus 77 days up to and including actual study day of week 24 visit minus 70 days
- Week 15 = Actual study Day of Week 24 visit minus 70 days up to and including actual study day of week 24 visit minus 63 days
- Week 16 = Actual study Day of Week 24 visit minus 63 days up to and including actual study day of week 24 visit minus 56 days
- Week 17 = Actual study Day of Week 24 visit minus 56 days up to and including actual study day of week 24 visit minus 49 days
- Week 18 = Actual study Day of Week 24 visit minus 49 days up to and including actual study day of week 24 visit minus 42 days
- Week 19 = Actual study Day of Week 24 visit minus 42 days up to and including actual study day of week 24 visit minus 35 days
- Week 20 = Actual study Day of Week 24 visit minus 35 days up to and including actual study day of week 24 visit minus 28 days
- Week 21 = Actual study Day of Week 24 visit minus 28 days up to and including actual study day of week 24 visit minus 21 days
- Week 22 = Actual study Day of Week 24 visit minus 21 days up to and including actual study day of week 24 visit minus 14 days
- Week 23 = Actual study Day of Week 24 visit minus 14 days up to and including actual study day of week 24 visit minus 7 days
- Week 24 = Actual study Day of Week 24 visit minus 7 days up to and including actual study day of week 24 visit
- For patients who discontinue the study before Week 24:
 - Week 1 = on or after Day 1 and up to and including Day 8
 - Week 2 = after Day 8 and up to and including Day 15

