For patients who permanently discontinue the study medication, the “Date of Visit X(n)”/ “Date of Visit Y” will be replaced by the last dose date of study medication, as specified in section 14 of the SAP. Whereas for patients who completed study, the “Date of Visit X(n)”/ “Date of Visit Y” will be replaced by date of last dose.

Drug intake as recorded in the e-diary: percent of ‘yes’ responses. The denominator is the number of records for which the patient provided an answer (Yes or No) to drug intake questions (morning and evening) in the e-diary.

For time interval study medication e-diary compliance, use week’s windowing conventions described in section 6.4 of the SAP. Use study day assigned to determine the date for weeks required or the time intervals, Week 12 and Week 24. The compliance will be calculated as follows:

$$\frac{(\text{Week X}^* < \text{number of 'yes' responses entered in the eDiary} \leq \text{Week Y})}{(\text{Week X}^* < \text{number of non - missing responses entered in the e - Diary} \leq \text{Week Y})} * 100$$

*If Week X = Day 1, update “<” to be “≤”. If Week Y is Week 24 and patient has completed treatment then the last entry we expect in the morning. Patient should not log any entries from and including evening of Week 24.

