16.2.1.2. Questionnaires

16.2.1.2.1. E-RS™:COPD

EXACT-Respiratory Symptoms for COPD (E-RS™: COPD) data will be collected within EXACT-PRO questionnaire (consisting of 14 questions), as shown in Appendix 3. Please note that items 3, 8, 9, 10, 11 and 14 have separate scoring instructions, namely with the same raw score being assigned to several answer options. E-RS™: COPD consists of 11 questions, with subdomains of: Breathlessness, Cough and Sputum, and Chest Symptoms. This data will be collected everyday throughout the duration of the study.

Calculating the score

E-RS subdomains:

- Breathlessness – items 7, 8, 9, 10 and 11 (score range: 0-17)
- Cough and Sputum – items 2, 3 and 4 (score range: 0-11)
- Chest Symptoms – items 1, 5 and 6 (score range: 0-12)

The E-RS Total score is derived as the sum of the raw scores of the 11 items (score range: 0-40). Total and subdomain scores are derived weekly as the mean over the days within each window, as specified in the section 6.4 of the SAP, using only days where data was recorded. Baseline is the mean over the 7 days prior to the first intake of study treatment, using only days where data was recorded. If less than 4 days of data are available for the week, the weekly mean is set to missing. Furthermore, all questions need to be answered to be evaluable for that day.

If a patient discontinued then use treatment study end date, as the date of their last expected visit.

The EXACT-PRO total score will be calculated by first summing the raw scores of all 14 items (score range: 0-51) and then looking up the corresponding EXACT-PRO total score in the table described in the APPENDIX 4 (converted score range: 0-100).

E-RS subdomain score is calculated as the sum from the relevant questions.

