16.2.1.3. Rescue Medications

Baseline use of rescue medication is the mean over the last 7 days of run-in phase, using only days where data was recorded:

$$\frac{\text{Sum of number of puffs taken}}{\text{days recorded}}$$

Use of medication per week is calculated as the mean use daily over 7 days, as described in the windowing conventions section of the SAP, calculated only based on the days data was recorded/verified.

If less than 4 days of data are available for the week, the weekly mean is set to missing.

If a patient discontinued then use study discontinuation end date, as the date of their last expected data input.

This will be documented as Albuterol/Salbutamol in the “Rescue Medication” page of the eCRF, as well as in the “Rescue Medication Use” diary entry.

The rescue medication use will be confirmed in the diary using the following rules:

1. If patient has put in rescue medication use then analyze as expected
2. If patient has not put in rescue medication use, then to confirm that there was no diary compliance issue, or IT issue, question “No Rescue Medication Confirmation” will be checked to make sure it is filled in correctly.
3. If patient has not put in rescue medication use and question “No Rescue Medication Confirmation” was not filled in correctly then this will be treated as diary compliance or IT issue and therefore this day will not be used as the day recorded for the weekly means calculation.

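### The Week 24 diary window includes the visit day, when treatment completers make no evening entry, so the Week 24 E-RS mean can use at most 6 days, against 7 at baseline and Weeks 6 and 12

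*SAP*

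**What the plan says.** SAP 6.4 counts diary weeks backwards from the Week 24 visit. The rule applies to this group: "For patients who completed the study or who discontinued study medication but continue in the study". Week 24 is "Week 24 = Actual study Day of Week 24 visit minus 7 days up to and including actual study day of week 24 visit". Week 23 runs from the visit day "minus 14 days up to and including actual study day of week 24 visit minus 7 days". Only Week 1 has its lower bound marked as included: "Actual study Day of Week 24 visit minus 168 days (inclusive) up to and including" visit day minus 161.

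Protocol 8.3.3.6 has the E-RS completed "in the form of the EXACT-PRO in the eDiary each evening before bedtime". SAP 15.1.1, on study-medication diary compliance, says that in a patient who completed treatment the last entry is expected on the morning of Week 24, and adds: "Patient should not log any entries from and including evening of Week 24".

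SAP 16.2.1.2.1 averages the E-RS over the recorded days in each window, with the rule "If less than 4 days of data are available for the week, the weekly mean is set to missing". Baseline is the mean over the 7 days before first intake. SAP 16.2.1.3 uses the same 4-day minimum for rescue medication and describes the weekly value this way: "Use of medication per week is calculated as the mean use daily over 7 days". Neither section makes an exception for Week 24.

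**The concern.** The window and the diary schedule do not fit together. The window's last day is the visit day, and for a treatment completer that day has no evening entry. One of the seven days is therefore empty by design, and the completeness rule becomes 4 of 6 at Week 24 while it is 4 of 7 at baseline and at Weeks 6 and 12.

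Week 24 is the time point tested for the E-RS, which is third in the hierarchy of SAP 7.4. Some completers with 3 recorded days in the shortened window would have reached 4 in a full week. They are instead set to missing and imputed, although the diary entry that would have qualified them was collected.

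**Working it through.** **1. Length of the diary week.** Take V = 169 as an example. Week 23 includes V-7, and only Week 1 has an inclusive lower bound, so Week 24 is V-6 to V, Days 163 to 169: 7 calendar days. This agrees with the fixed windows in SAP 6.4 for early leavers, where Week 24 starts after Day 162 and ends on Day 169. Weeks 2 to 24 have 7 days each and Week 1 has 8 (Days 1 to 8). The total is 8 + 23 × 7 = 169, so each day is assigned once. The 7-day week described for rescue use is reproduced.

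**2. Evenings that can carry an E-RS entry.**

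| Period | Days | Possible evening entries |
|---|---|---|
| Baseline | 7 days before first intake | 7 |
| Week 6 | V-132 to V-126 | 7 |
| Week 12 | V-90 to V-84 | 7 |
| Week 24 | V-6 to V, no entry on the evening of V | 6 |

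**3. If both bounds were inclusive.** Week 24 would be V-7 to V, which is 8 days with 7 evenings. But V-7 would then fall in both Week 23 and Week 24, and the other weeks would hold 8 evenings. Week 24 would still be one short of them.

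**4. Effect of the 4-day minimum.** Let p be the chance that a possible entry is made, independent across days. The documents give no completion rate, so p is an assumption. The weekly mean is missing when X < 4, with X binomial (n, p). The extra missingness from losing one day is

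P(X₆ < 4) − P(X₇ < 4) = p × P(X₆ = 3).

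Only patients with exactly 3 entries in the six evenings, plus an entry on the seventh, change status. At p = 0.90 this is 0.90 × 20 × 0.9³ × 0.1³ = 0.0131.

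| p | 7 possible days | 6 possible days | Difference (points) |
|---|---|---|---|
| 0.95 | 0.02% | 0.22% | 0.20 |
| 0.90 | 0.3% | 1.6% | 1.3 |
| 0.80 | 3.3% | 9.9% | 6.6 |

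If all 800 planned patients completed, which is an upper limit, the differences would be about 800 × 0.0020 = 2, 800 × 0.0131 = 10 and 800 × 0.0655 = 52 patients over both arms.

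**5. Without a common completion rate.** If p varies between patients as a beta distribution with mean 0.85 and a + b = 5 (also an assumption), the shares are 6.6% with 7 possible days and 11.0% with 6.

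**The case against.** The case against giving this weight is that it is a small matter of definition. Much of that stands.

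- **No bias is shown.** Weekly means use recorded days only, and the rule is the same in both arms. Patients set to missing are imputed with their other weekly means in the model (SAP 16.2.2.1). A reader might infer a distorted treatment difference, but the documents do not support that.
- **The entry at V-7 is not thrown away.** It belongs to Week 23, and the first imputation step for weekly endpoints uses all available weeks. It is lost only to the observed Week 24 mean.
- **Rescue use is less clear.** A reader might infer that the rescue mean is also capped at 6 days. Protocol 6.7.1.1 puts rescue use during spirometry visits in an eCRF module, and SAP 16.2.1.3 names the eCRF page as a source beside the diary. A partial visit day could count as the seventh; the SAP does not say. The limit is likely for evening diary entries but not established.
- **Scope.** The no-entry sentence sits in the medication-compliance section and covers patients who completed treatment. Patients off drug but still in the study share the window but are not named there. The Schedule of Activities appears to have the eDiary collected at the Week 24 visit, which would cover them too, but the layout of that table is unclear and the point does not rest on it.
- **Very low completion rates.** At 70% completion the shares would be 12.6% and 25.6%. Nothing in the documents supports that rate. Randomization requires 5 of the last 7 run-in days (71%) from every patient, and sites review diary compliance at clinic visits.
- **The windows are shared.** SAP 6.4 uses them for COPD exacerbations and other diary data as well. Moving them for every purpose would leave visit-day exacerbation data, and the expected morning medication entry, outside Week 24.

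What remains is the count for the E-RS. The morning entry expected on the visit day does not change it, because the protocol places the E-RS in the evening.

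**Conclusion.** The point holds for the E-RS in treatment completers: at most 6 usable days at Week 24, against 7 at baseline and Weeks 6 and 12, with the same 4-day minimum. The consequence is slightly more avoidable missingness at the tested time point. It is negligible at 95% daily completion, 1.3 percentage points at 90%, and 6.6 points at 80%. These sizes rest on assumed completion rates and on independence between days. The day count itself rests on reading the lower bounds of Weeks 2 to 24 as exclusive, which follows from the Week 23 rule and from Week 1 alone being marked inclusive. For rescue use, the finding is only that the SAP does not say whether the partial visit day counts. This is a cheap improvement, not a threat to the trial's conclusions.

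**What to change.** In SAP 6.4, add a separate rule for the E-RS and rescue weekly means in patients with a Week 24 visit. Define Week 24 as V-7 to V-1 and move each earlier week back by one day, so that Week k runs from V − 7(25 − k) to V − 7(24 − k) − 1. With V = 169, Week 24 becomes Days 162 to 168 and Week 1 becomes Days 1 to 7. All 24 weeks then hold 7 evenings (24 × 7 = 168), matching the baseline, and Week 1 no longer has 8 days. The rule also settles the handling of rescue use on the Week 24 visit day, which would not count.

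Keep the 4-day minimum. Leave the present windows in place for COPD exacerbations and study-medication diary compliance.

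The cost is one SAP paragraph and a one-day shift in the derivation of these endpoints; no new data are needed. The small downside is a second window definition that, at V = 169, sits one day earlier than the fixed windows for early leavers.

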6.5. STATISTICAL TESTS

In general, unless stated otherwise, continuous variables will be summarized using descriptive statistics (number of patients, mean, standard deviation [SD], median, minimum and maximum values) and for categorical (nominal) variables, the number and percentage of patients will be used.

The default significant level will be 5%; CIs will be 95% and all tests will be two-sided, unless otherwise specified in the description of the analyses.

6.6. COMMON CALCULATIONS

- Change from baseline: Test Value at Visit X – Baseline Value
- Percentage change from baseline:

$$\frac{\text{Test Value at Visit X} - \text{Baseline Value}}{\text{Baseline Value}} * 100\%$$

6.7. ACTUAL TREATMENT

Once the study unblinds, the patient's actual treatment will be assigned based on the most frequent medication they have received throughout the study. Patients are only expected to receive either 3 mg of ensifentrine, or placebo. The external vendor, Cenduit, will provide the Material List document after confirmation of a DBL. This document will contain the kit

numbers, which will be merged with the site data to obtain the treatment that was dispensed at each visit.

If a patient takes more than one medication and the ratio of actual treatments taking the placebo and ensifentrine is the same, then the patient will be assigned ensifentrine.

6.8.SOFTWARE VERSION

All analyses will be conducted using SAS version 9.4 or higher.

6.9.STRATA CALCULATIONS

There are two separate stratification factors used: background maintenance therapy strata and smoking strata. For both factors planned and actual will be created.

For background maintenance therapy strata:

- Planned – As recorded in the Cenduit report.
- Actual - As recorded in the “Concomitant medications” eCRF page: Patients that take LAMA or LABA (or LAMA/ICS or LABA/ICS) medication with start date being before or on randomization date and end date is either ongoing/post-randomization are classified as being on background maintenance therapy strata. Patients that do not meet this criteria will be classified as “No”.

For smoking strata:

- Planned – As recorded in the Cenduit report.
- Actual – As recorded in the “COPD and Smoking History” eCRF page.

7. STATISTICAL CONSIDERATIONS

7.1.ADJUSTMENTS FOR COVARIATES AND FACTORS TO BE INCLUDED IN ANALYSES

The following covariates and factors are used in the analyses. For details of their inclusion in the models, see the specific analysis section.

- Fixed effects: treatment (ensifentrine, placebo), region (Europe, North America), visit (Day 1, Week 6, Week 12, Week 18, Week 24), visit*treatment, stable background maintenance of LABA or LAMA (or LAMA/ICS or LABA/ICS) therapy use (yes, no), cigarette smoking (current, former)

- Random effect: patient
- Covariate: baseline

7.2. MULTICENTER STUDIES

This study will be conducted by multiple investigators at multiple centers internationally. Randomization to treatment arms is not stratified by country/ center.

When specified, statistical analysis will be adjusted for geographic region. Geographic region will be categorized as shown in Table 3:.

Table 3: Geographic Regions

Geographic Region	Country
Europe	Belgium, Bulgaria, Denmark, Hungary, Poland, Slovakia, Estonia, Spain
North America	United States, Canada

7.3.MISSING DATA

Missing safety data will not be imputed.

All data collected during the scheduled visits for patients on-treatment and off-treatment, for patients with treatment withdrawal, as well as the end-of-study visits for patients withdrawing from the study will be used for analysis performed on the mITT and that the remaining missing values will be handled as described in sections 16.1.2, 16.2.2 and 16.3.2 of the SAP.

7.4.MULTIPLE COMPARISONS/ MULTIPLICITY

To address multiplicity in the analysis of the endpoints, statistical testing of the primary endpoint and key secondary endpoints will be done in the hierarchical order (listed below). Initially the primary endpoint will be checked to see if comparison between active treatment and placebo is statistically significant. If yes, the first key secondary endpoint will be evaluated. If yes, the next key secondary endpoint will be evaluated. This process will continue until either all endpoints are evaluated, or if one of the endpoints' comparison is not significant.

Order of the endpoints that will be used for the hierarchical testing:

1. Change from baseline FEV₁ to FEV₁ AUC_{0-12h} at Week 12
2. Change from baseline FEV₁ to peak FEV₁ at Week 12
3. Change from baseline (i.e. mean over the last 7 days of run-in) to the mean weekly value at Week 24 in COPD symptoms, as measured by daily diary (E-RSTM:COPD)
4. Change from baseline in the SGRQ total score at Week 24
5. Change from baseline FEV₁ to morning trough FEV₁ at Week 12
6. Change from baseline FEV₁ to average FEV₁ AUC_{0-4h} at Week 12
7. Proportion of SGRQ responders at Week 24

7.5.EXAMINATION OF SUBGROUPS

Subgroup analyses will be conducted as stated in the efficacy analysis and disposition sections. Primary aim for the subgroup analysis is to check whether there are differences in treatment effect between strata or subgroups, which will be tested through interaction. For each analysis

by subgroup the results will be summarized as follows:

- Complete data with added fixed effect to the model: subgroup*treatment.
- Data split by subgroup using the main model.

The following subgroups will be assessed and described within the analysis sections 16.1.4 and 16.2.4 of the SAP.

- Gender at birth:
 - Female
 - Male
- Age-class (years):
 - <65
 - ≥65
- Region
 - Europe
 - North America
- Actual Background medication strata
 - Yes
 - No
- Actual Smoking strata
 - Current
 - Former
- Actual ICS use
 - Yes
 - No
- Known chronic bronchitis
 - Yes
 - No
- FEV₁ reversibility at screening (≥12% and ≥200mL increase in FEV₁)
 - Yes
 - No
- COPD severity
 - Moderate (50% ≤ post-bronchodilator FEV₁ at screening < 80% predicted)
 - Severe (30% ≤ post-bronchodilator FEV₁ at screening <50% predicted)
 - Very severe (post-bronchodilator FEV₁ at screening <30% predicted)

